#### Immunologic Responder Definitions

*Serology*: Serum samples will be assayed for antibody IgG and IgA titers against LT and CS6 using ELISA methods previously established in the NMRC Immunology Laboratory. Previously established high-titer specimens will be included on each plate to track day to day interassay variation. For each antigen, pre- and post-vaccination serum samples will be assayed concurrently. The antibody titer assigned to each sample will represent the geometric mean of duplicate tests performed on two different days. Seroconversion will be defined as a  $\geq 4$ -fold increase in endpoint titer between pre- and post- vaccination samples and a post-vaccination reciprocal titer greater than 10. A 4-fold rise is calculated by dividing the post-challenge reciprocal endpoint titer by the day pre-challenge reciprocal endpoint titer. Once a subject is defined as 'immunologic responder', that person is permanently categorized as a 'RESPONDER'. All statistical analyses will be performed on  $\log_{10}$  – transformed titer values. Titers will be displayed graphically as  $\log_{10}$  reciprocal endpoint titers or geometric mean titers. For subjects with a reciprocal titer less than 5, they will be assigned a value of 2.5 for computational purposes.

*Antibody in Lymphocyte Supernatants (ALS)*: Peripheral Blood Mononuclear Cells (PBMCs) will be collected to determine antibody responses from Lymphocyte Supernatant against CS6 and LT. Antibody in Lymphocyte Supernatant (ALS) is an indirect quantification of antibody secreting cells (ASC) activated in the mucosa that circulate in the peripheral blood about seven days post-mucosal immunization/infection. This method has been shown to be a replacement for ELISPOT methodology. PBMCs are incubated without stimulation and the supernatant is later assayed for antigen-specific IgG and IgA Abs by ELISA. Seroconversion will be defined as a  $> 4$ -fold increase in endpoint titer between pre- and post- challenge samples. A 4-fold rise is calculated by dividing the post vaccination reciprocal endpoint titer by the pre-vaccination reciprocal endpoint titer. Once a subject is defined as 'immunologic responder', that person is permanently categorized as a 'RESPONDER'. All statistical analyses will be performed on  $\log_{10}$  – transformed titer values. Titers will be displayed graphically as  $\log_{10}$  reciprocal endpoint titers or geometric mean titers.

#### Exploratory Endpoints and Responder Definitions

Stool and saliva samples will be collected to explore the antigen-specific IgA response at the mucosal level by measuring IgA antibody titers against CS6 and LT. Immunologic responders will be defined as subjects with a  $>$  two-fold increase in reciprocal endpoint titer.

*Saliva IgA*: Total IgA content in the saliva extract samples will be determined by a modified ELISA method using commercial purified total IgA standard. Specimens with IgA concentration  $< 10$   $\mu\text{g/ml}$  will be excluded from further analysis, since antibody

titrations of specimens with such low IgA content give unreliable results. Subsequently, no comparison to post-immunization values will be performed. Specific antibody levels in the salivary extracts will be determined using similar ELISA methods described above. Salivary antibodies will be reported as adjusted end-point titers. Adjusted end-point titers will be calculated by dividing the antigen specific reciprocal titer value by the Total IgA reciprocal titer value. A  $\geq 4$ -fold increase in the specific IgA per total IgA content between pre- and any post-vaccination specimens is considered a responder. All statistical analyses will be performed on  $\log_{10}$  – transformed titer values.

*Fecal IgA:* Stool samples will be collected by subjects to assess fecal IgA immune responses. Total IgA content in the fecal extract samples will be determined by a modified ELISA method using commercial purified total IgA standard. Specific antibody levels in the fecal extracts will be determined using similar ELISA methods described above. Fecal antibodies will be reported as adjusted end-point titers. A  $\geq 4$ -fold increase in the specific IgA per total IgA content between pre- and any post-vaccination specimens is considered a responder. All statistical analyses will be performed on  $\log_{10}$  – transformed titer values.

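### Both mucosal IgA responder rules (saliva and stool) lack a minimum antigen-specific titer, so a fall in total IgA alone can make a subject a responder

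*SAP*

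**What the plan says.** The SAP's Section 8, under Exploratory Endpoints and Responder Definitions, treats saliva and stool in parallel paragraphs.

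- **Ratio.** The formula is written out under saliva: "Adjusted end-point titers will be calculated by dividing the antigen specific reciprocal titer value by the Total IgA reciprocal titer value". The stool paragraph uses the same term ("Fecal antibodies will be reported as adjusted end-point titers").
- **Responder rule.** For both sample types, a 4-fold or greater "fold increase in the specific IgA per total IgA content between pre- and any post-vaccination specimens is considered a responder". No minimum specific titer is attached to either.
- **Low-IgA specimens.** Saliva below 10 µg/ml IgA "will be excluded from further analysis, since antibody" "titrations of specimens with such low IgA content give unreliable results". The stool paragraph measures total IgA ("Total IgA content in the fecal extract samples will be determined by a modified ELISA method using commercial purified total IgA standard") but states no minimum.
- **Serum, for comparison.** Under Immunologic Responder Definitions, seroconversion needs a 4-fold or greater rise and also "a post-vaccination reciprocal titer greater than 10". Reciprocal titers below 5 are set to 2.5; this is stated for serology only.
- **A second mucosal threshold.** The opening lines of the exploratory subsection define a mucosal responder by a more than two-fold rise in the reciprocal endpoint titer, with no mention of total IgA.

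Table 8 reports the number and percentage of salivary and fecal responders to LT and CS6, by group.

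**The concern.** A ratio can rise because its numerator rises or because its denominator falls. Only a rise in the numerator shows that antigen-specific antibody has appeared. When the specific titer is undetectable before and after vaccination, the numerator is a placeholder and the whole change comes from total IgA. The serum rule guards against calling a response on trivial titers; the mucosal rules do not.

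Among subjects with no specific response, the error can only add responders. Any single post-vaccination specimen may qualify a subject, so each further sample adds another chance. Total IgA is one value per specimen, so one low value can create a response to LT and to CS6 together. Groups B to E have 10 subjects and the two parts of Group A have 5 each (SAP Table 2). One false responder therefore moves a Table 8 percentage by 10 or 20 points.

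**Working it through.** The SAP gives no figure for this endpoint, so there is nothing to reproduce. The check has four steps.

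**1. The ratio with a flat numerator.** Let S be the specific titer and T total IgA. The fold change is F = (S_post / T_post) / (S_pre / T_pre). If S_pre = S_post, then F = T_pre / T_post, whatever the floor value is.

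| T_pre | T_post | F | Responder at 4-fold or more? |
|---|---|---|---|
| 40 | 8 | 5.0 | yes |
| 40 | 10 | 4.0 | yes |
| 40 | 11 | 3.6 | no |
| 100 | 20 | 5.0 | yes |

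The serology floor of 2.5 gives the same answer: (2.5/8) / (2.5/40) = 5.0.

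**2. How often this could happen.** Assumptions, none of them from the SAP: specific titer at a constant floor at every visit, log-normal total IgA with no true change over time, and within-subject SD σ on the log10 scale. A false response needs log10 T_pre − log10 T_post ≥ log10 4 = 0.602.

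For one post-vaccination sample, the probability is 1 − Φ(0.602 / (σ√2)). At σ = 0.2 this is 1 − Φ(2.13) = 1.7%; at σ = 0.3 it is 1 − Φ(1.42) = 8%. For three samples, any one of which may qualify, the probability was found by simulation and confirmed by numerical integration over the baseline value.

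| σ (log10) | False responders, 3 post samples | Expected among 10 such subjects |
|---|---|---|
| 0.2 | 4% | 0.4 |
| 0.3 | 18% | 1.8 |
| 0.4 | 30% | 3.0 |
| 0.5 | 38% | 3.8 |
| 0.6 | 45% | 4.5 |

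These are rates per antigen, among subjects with no detectable specific IgA at any visit. Requiring a detectable post-vaccination titer takes them to 0% by construction.

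**3. Whether the saliva exclusion would cure it in stool.** It would do so only in part. The fall from 100 to 20 passes a 10 µg/ml cut-off and still gives F = 5. With three post samples and σ = 0.4, the rate among evaluable subjects goes from 29.7% to 28.6% if median total IgA is assumed to be 100 µg/ml, and from 30% to 18% at an assumed median of 30 µg/ml. The loss of specimens can be large: at median 30 and σ = 0.6, z = log10(10/30) / 0.6 = −0.477 / 0.6 = −0.80, so about 21% of specimens fall below the cut-off.

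**4. The two thresholds.** Under the opening two-fold sentence, read literally on the unadjusted titer, a flat specific titer gives a fold change of 1 and is never a response. Under the 4-fold rule on the ratio it can be. If the two-fold threshold were applied to the ratio, a fall in total IgA of just over 2-fold would be enough (45% at σ = 0.3 with three samples). The internal conflict therefore decides whether the artefact arises at all and how large it is.

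**The case against.** Several objections carry weight.

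- **Normalising to total IgA is legitimate.** It is, and it allows for differences in specimen yield. But a ratio with an undetectable numerator carries no information about specific antibody, and the objection does not reach that case.
- **The size is assumption-driven.** This stands. The SAP gives neither the variability of total IgA nor the number of samples, and the share of subjects with undetectable specific IgA is unknown.
- **The floor is itself assumed.** The 2.5 substitution is written for serum only. Some positive value is nevertheless needed for log10 analysis, and any constant cancels. The saliva formula names a total-IgA titer rather than a concentration; the algebra is the same on either scale.
- **The endpoint matters little.** SAP Section 4.2 puts exploratory objectives outside the plan's scope, escalation rests on safety alone (Section 5), and the trial is not designed to show group differences (Section 6). This lowers the severity. It does not remove the point, because the plan defines the rule and includes a table for it.

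A reader might infer that the fault is the missing low-IgA exclusion for stool. The document does not support that. The exclusion is justified by unreliable titration, not by movement of the denominator; it would leave much of the artefact in place; and saliva, which has the exclusion, is exposed too. Nor does silence on a fecal minimum show that every stool specimen is kept, since assay acceptance limits may sit in the protocol or laboratory procedures.

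**Conclusion.** The point holds for saliva and stool alike. As written, the 4-fold rule on the ratio can classify a subject as a responder on a fall in total IgA alone, because no detectable specific titer is required. The algebra is certain. The frequency is not: 4% to 45% rests on an assumed SD of 0.2 to 0.6 log10, three post-vaccination samples and a specific titer at the floor throughout. It should not be read as the bias in Table 8, which depends on how many subjects are in that position.

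Nothing in the SAP supports 10 µg/ml as the right limit for fecal extracts, so the saliva value should not simply be carried over. Severity is minor: the endpoint is exploratory, does not drive escalation, and is accompanied by quantitative log10 analyses.

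**What to change.** **Main change, for both saliva and stool.** Add to each responder rule: *and the post-vaccination antigen-specific titer in the specimen showing the rise must be above the lower limit of the assay.* This mirrors the serum rule and uses data already collected. It does not cover a subject whose specific titer is detectable but flat; excluding that case would need a required rise in the unadjusted titer.

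**In the same edit.** Reconcile the more-than-two-fold sentence on the endpoint titer with the 4-fold rule on the adjusted titer, so that one definition governs Table 8.

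**Secondary.** The plan calls low-IgA saliva titrations unreliable, so it should state whether a total-IgA minimum applies to stool. If one does, the laboratory should fix it for fecal extracts before the assays are run, and exclusions should be reported per cohort.

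**Cost.** One sentence for the main condition, one correction and one clarification, with no new assay. Responder rates will be slightly lower. A fecal minimum, if adopted, may lose a non-trivial share of stool specimens, and losing a baseline specimen removes that subject from the comparison.

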## 9 Figures

Sample data tables and figures are included below to guide through the analysis and data presentation. Final tables and figures may be modified to optimize data presentation.

### Results

**Table 3: Demographic characteristics of study subjects**

Characteristic	Participant (n =)	Screened (Not Enrolled)
Mean Age (sd)*	0	0
Age range	-	-
Gender (%)		
Male	0	0
Female	0	0
Race/Ethnicity		
African-American	0	0
Caucasian	0	0
Asian-American	0	0
Other	0	0

\*Measured in mean (standard deviation)

**Table 4:** Baseline characteristics of study participants (by cohort)

Cohort	A		B	C	D	E
	A-1	A-2				
Age a						
Gender [N (%)]						
Male						
Female						
Race/Ethnicity [N (%)]						
African-American						
White						
Asian						
Other						
LT IgA						
LT IgG						
CS6 IgA						
CS6 IgG						

a Presented as mean (standard deviation) or median (interquartile range)

**Table 5.** Safety profile of all adverse symptoms coded as ‘related’ to vaccine following vaccination [n(%)] (Groups compared using a Chi-squared analysis)

AE	Cohort A			Cohort B			Cohort C			Cohort D			Cohort E		
Dose	1	2	3	1	2	3	1	2	3	1	2	3	1	2	3
AE1															
AE2															
AE#															

**Table 6.** Safety profile of all adverse symptoms coded as ‘unrelated’ to vaccine following vaccination [n(%)] (Groups compared using a Chi-squared analysis)

AE	Cohort A			Cohort B			Cohort C			Cohort D			Cohort E		
Dose	1	2	3												
AE1															
AE2															
AE#															

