## **5 Study Methods**

This is an open-label Phase 1 clinical trial of CssBA±dmLT in which a total of 50 subjects will receive three vaccinations via IM injection on days 1, 22, and 43 (See Table 2). Dose escalation of CssBA from 5µg to 15µg to 45µg, and dmLT from 100 to 500ng will take place as outlined below. Group A is considered a pilot group in which CssBA and dmLT will be administered separately. All 3 doses will be administered and subjects monitored for safety 7 days after the third vaccination, prior to the enrollment of subjects in Group B.

The decision to advance to the next group will be based solely on the safety assessment. A dose level with no occurrence of stopping criteria will prompt moving to the next higher level. All safety data will be summarized and reviewed with the SRC prior to advancing to dose escalation.

Approximately one week after the first group (Group A) receives the third vaccination dose (Day 49), an interim Safety Report will be prepared by the PI and Study Statistician for review by the SRC. The content of the report will be agreed upon by the PI and the SRC and will include, but not be limited to, all adverse events (solicited, unsolicited, expected and unexpected) as well as relevant safety endpoints. Advancement to Group B will be based entirely on this safety assessment. The SRC's concurrence to advance to the next group will be made and provided in written format. This process will be repeated after groups B, C, and D before enrollment for the next group.

dmLT will be administered at the 500 ng dose in groups D and E if no significant reactogenicity is observed in Group C.

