**Table 2. Study Design of Phase 1 Clinical Trial of Intramuscularly Administered CssBA with dmLT (N=50)**

Group	N	Route	CssBA (µg)	dmLT (ng)
A	5	IM	5	0
	5	IM	0	100
B	10	IM	5	100
C	10	IM	5	500
D*	10	IM	15	100/500
E*	10	IM	45	100/500

\*Plan to proceed with 500ng dose; however, if there is an aberrant safety signal in Group C, will proceed with the 100 ng dose (presuming no prior signal in Group B)

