The proportion of all subjects with each AE will be summarized with point estimate for percent and 95% confidence intervals calculated using valid asymptomatic and/or exact binomial estimates. Summary tables will be created which will describe the number and percentage of subjects who experience each adverse event. In addition, tables will be prepared to list each adverse event, the number of subjects experiencing an event at least once, and the proportion of subjects with adverse event(s). Adverse events will be divided into defined severity grades (mild, moderate, severe, or potentially life-threatening). The tables will also divide the adverse events by severity and related (definite, probable, possible) or unrelated (unlikely, not related) to the investigational product.

All subjects who receive vaccination will be included in the safety analysis. Adverse event data will be listed individually and summarized by body system and preferred terms within a body system for each treatment group. Serious and/or unexpected AEs will also be discussed on a case-by-case basis. For the tabulation of the AEs by body system, a subject will be counted only once in a given body system. For example, a subject reporting nausea and diarrhea will be reported as one subject, but the symptoms will be listed as two separate AEs within the class. Therefore the total number of AEs reported within a body system may exceed the number of subjects within the body system reporting AEs.

Rates of all adverse events will be analyzed by Pearson's Chi-square test (or Fisher's exact test if assumptions are not met for Pearson's Chi-square) to compare dose levels. Summary tables will be created which will indicate the number of subjects who experienced events. Vaccine-related events (probably or possibly related) will be tabulated by study group. In addition, tables will be prepared to list each adverse event, the number of subjects in each treatment group who experienced an event at least once, and the rate of subjects with adverse event(s). Adverse events will be divided into defined severity grades (mild, moderate, severe). The tables will also divide the adverse events by severity and relationship to the investigational product. All immunized subjects will be included in the safety analysis.

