**Immunology**

**Table 7: Serological Immunological Responses to LT and CS6**

Cohort		LT				CS6			
		ALS		Serum		ALS		Serum	
		IgG	IgA	IgG	IgA	IgG	IgA	IgG	IgA
		A	A-1						
	A-2								
	B								
	C								
	D								
	E								

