**Table 8: Saliva and Fecal Immunological Responses to LT and CS6**

Group		Number of Volunteers (%)			
		LT		CS6	
		Salivary IgA	Fecal IgA	Salivary IgA	Fecal IgA
A	A-1				
	A-2				
B					
C					
D					
E					

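### The end-of-study adverse event tables (SAP Tables 5 and 6) pool the antigen-only and adjuvant-only halves of Group A into one Cohort A column, unlike the plan's other by-cohort tables

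*SAP*

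**What the plan says.** SAP Section 5 describes the first group thus: "Group A is considered a pilot group in which CssBA and dmLT will be administered separately". Table 2 ("Study Design of Phase 1 Clinical Trial of Intramuscularly Administered CssBA with dmLT (N=50") gives it two rows: 5 subjects with 5 µg CssBA and no dmLT, and 5 subjects with 100 ng dmLT and no CssBA. Groups B to E have 10 subjects each and receive both components.

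The shells in Section 9 treat Group A in two ways:

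- Table 4 ("Baseline characteristics of study participants (by cohort"), Table 7 ("Serological Immunological Responses to LT and CS6") and Table 8 ("Saliva and Fecal Immunological Responses to LT and CS6") each divide it into A-1 and A-2.
- Tables 5 and 6, for related and unrelated AEs, have one Cohort A, subdivided only by dose 1, 2 and 3. Their captions name the test: "to vaccine following vaccination [n(%)] (Groups compared using a Chi-squared analysis".

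The interim forms in Section 10 list A-1 and A-2 as separate cohorts.

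Section 7.1.1 says "Rates of all adverse events will be analyzed by Pearson's Chi-square test", with Fisher's exact test when the Pearson assumptions are not met, and gives comparison of dose levels as the purpose. It also promises a tabulation of "the number of subjects in each treatment group who experienced an event at least once". It does not say whether Group A counts as one treatment group or two. The omnibus null hypothesis in Section 3 carries Cohort A as a single parameter.

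**The concern.** A-1 and A-2 share no product. A rate formed over their 10 subjects is not the rate for any treatment in Table 2, and it is not a dose level in the sense that Section 7.1.1 needs for its test.

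The primary objective is the safety of CssBA with and without dmLT. A-1 is the only arm without dmLT, and A-2 is the only arm without CssBA. Group B (5 µg CssBA plus 100 ng dmLT) differs from A-1 by the adjuvant and from A-2 by the antigen. Once A-1 and A-2 are merged, neither comparison can be read from the final AE tables. A difference between the halves can also average out in the pooled cell and drop out of the test that the captions announce.

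**Working it through.** **Inputs.** The arm sizes come from Table 2. The SAP gives no AE counts, so every count below is assumed for illustration.

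**Sample size.** 5 + 5 + 10 + 10 + 10 + 10 = 50, which matches the total in Table 2. A single Cohort A column therefore has denominator 5 + 5 = 10.

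**Is the merge real?** The dose row of Table 5 has 15 entries, which is 5 cohorts × 3 doses. Six arms would need 6 × 3 = 18. Table 6 has the same five-cohort header.

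**What pooling does to the displayed rate.** Intervals are Clopper-Pearson 95%; p-values are two-sided Fisher for A-1 against A-2.

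| A-1 | A-2 | Pooled cell | Fisher p |
|---|---|---|---|
| 0/5 (0 to 52.2%) | 5/5 (47.8 to 100%) | 5/10 = 50% (18.7 to 81.3%) | 0.008 |
| 0/5 (0 to 52.2%) | 4/5 (28.4 to 99.5%) | 4/10 = 40% (12.2 to 73.8%) | 0.048 |
| 0/5 (0 to 52.2%) | 3/5 (14.7 to 94.7%) | 3/10 = 30% (6.7 to 65.3%) | 0.17 |
| 1/5 (0.5 to 71.6%) | 4/5 (28.4 to 99.5%) | 5/10 = 50% (18.7 to 81.3%) | 0.21 |

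Swapping A-1 and A-2 in any row leaves the pooled cell unchanged, so the cell cannot say which component produced the events. As a hand check of the second row, 2 × C(5,4)/C(10,4) = 2 × 5/210 = 0.048.

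**What pooling does to the overall test.** Take the extreme case of 0/5 in A-1, 5/5 in A-2 and 5/10 in each of B to E.

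- Pooled, five columns: every column is 5/10, so chi-square = 0.0 on 4 df, p = 1.00.
- Split, six columns: the overall rate is 25/50, so each of the four Group A cells has expected count 2.5. Chi-square = 4 × (2.5²/2.5) = 10.0 on 5 df, p = 0.075.

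**Which test will apply.** The SAP states no expected-count rule. Under the common criterion of at least 5 per cell, taken here as an assumption, an arm of 5 always fails because its two expected counts sum to 5. An arm of 10 passes only when the overall event rate is exactly 50%. Fisher's test will therefore be the usual outcome with or without the split, yet the captions of Tables 5 and 6 name only chi-squared.

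**Precision after the split.** For zero events the upper limit is 1 − 0.025^(1/n). This is 52.2% for n = 5 and 30.8% for n = 10.

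**The case against.** Section 9 offers the shells as samples that can be modified, and no sentence in the SAP orders A-1 and A-2 to be pooled. The text speaks of treatment groups, and since the two halves receive different products, a programmer could already read it as calling for separate columns. This stands to the extent that the SAP is ambiguous and does not expressly prescribe pooling. The ambiguity still matters: the shells are meant to guide the analysis, they show one column, and the omnibus hypothesis does the same.

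A reader might infer that the component safety data are lost, or that escalation would rest on a pooled rate. The documents do not support either. AEs are also listed individually. The interim forms are completed for A-1 or A-2, by dose and for the three-dose series, by grade and relatedness, and the Safety Review Committee reviews the interim report before Group B enrols. Those forms list a fixed set of 11 symptoms and carry no between-group test, so they do not replace the final tables.

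A reader might also infer that Group A exists to give a formal antigen-versus-adjuvant contrast. The SAP calls it a pilot group and states no such test. Sections 3 and 6 say that the trial is built for estimation and not to show differences between groups.

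Finally, the caption might be taken to mean that an invalid test is prescribed. Section 7.1.1 already supplies the Fisher fallback, so the caption is incomplete and no new method is needed.

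**Conclusion.** The inconsistency is real and concerns the primary safety objective. If followed as drawn, Tables 5 and 6 would report for Group A a rate out of 10 that belongs to no treatment, and would leave the A-1 and A-2 comparisons with Group B out of the final AE tables. The conclusion is limited to those two tables and the comparison run on them; it does not extend to the individual listings or the interim review.

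The benefit of correcting it is mainly descriptive. With 5 subjects per half, only near-complete separation reaches p < 0.05: under assumed counts 0/5 against 4/5 does (p = 0.048), while 0/5 against 3/5 (p = 0.17) and 1/5 against 4/5 (p = 0.21) do not. In a trial designed for estimation, a correct description by arm is nonetheless the main safety output.

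**What to change.** - In Tables 5 and 6, replace the Cohort A columns with A-1 and A-2 (N = 5 each), as in Tables 4, 7 and 8.
- In Section 7.1.1, state that A-1 and A-2 enter the AE comparison as separate arms, and make the Section 3 omnibus hypothesis agree for AE outcomes.
- Align the captions of Tables 5 and 6 with Section 7.1.1: Pearson's chi-square, or Fisher's exact test when its assumptions are not met, which will be usual with arms of 5 and 10.

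The work is two table shells, a short text edit and one programming change, with no new data. The statistical cost is wider intervals for the two Group A arms, which reflect the 5 subjects who actually received each product.
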